11.3.2. Secondary Efficacy Analysis

The secondary efficacy outcomes include:

- -
- Other Gastroparesis Core Symptoms: vomiting, early satiety, post-prandial fullness, and upper abdominal pain;
- Gastroparesis Cardinal Symptom Index (GCSI, calculated out of PAGA-SYM)
- PAGA-SYM
- Global Assessment of Gastroparesis
- Patient Rated Change in Gastroparesis Symptoms
- PGI-C
- PAGA-QOL
- GTBS
- CGI-S

Continuous endpoints will be summarized and analyzed in a manner similar to the primary endpoint. Details of the analysis will be described in the SAP.

Categorical variables will be evaluated as described in the SAP. Time to event data will be analyzed using the Kaplan-Meier method, and the treatment group differences will be tested by the log-rank test. Details of the analysis will be described in the SAP.

11.4. Safety Data Analysis

The primary assessment of safety will be based on the frequency of treatment-emergent adverse events (TEAEs), serious adverse events (SAEs) and on the frequency of clinically notable abnormal vital signs, electrocardiograms (ECGs) and laboratory values. Other safety evaluations include changes in vital signs, changes in clinical laboratory evaluations, and changes in ECGs, physical exam findings during treatment, and suicide ideation and behavior events.

11.4.1. Adverse Events

Adverse events will be recorded throughout the study and at early discontinuation. Adverse events and medical conditions will be coded using the Medical Dictionary for Regulatory Activities (MedDRA) coding dictionary. Treatment-emergent adverse events will be defined as those events, which are newly occurring or worsening from baseline. In all cases only treatment emergent adverse events will be summarized.

Treatment-emergent adverse events will be summarized within each treatment group by primary system organ class (SOC) and preferred term. (***NOTE***: In any given category [e.g. body system] a subject will only be counted once.) The incidence rates of TEAEs will be analyzed as described in the SAP. Similar displays will be provided for SAE and prior (conditions ending prior to the first dose of study medication and current (conditions present while on study medication) medical conditions.

Adverse events will further be categorized by severity, relationship to study medication, and action taken. Other information collected will be listed, as appropriate. Any event starting more than 3 days after the final dose of study medication will be excluded from the above tables and only listed, unless the event caused discontinuation.

The proportions of subjects experiencing SAEs and AEs resulting in discontinuation from the study will be summarized by treatment groups.

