
Overall Design:
 
This is a multicenter, randomized, double-blind, placebo-controlled study to be conducted in the United States. Up to eight hundred (800) subjects diagnosed with gastroparesis, who satisfy the selection criteria for the study, will be eligible for one of two groups. Group 1 will enter the Evaluation Phase of the study and Group 2 will enter the Open Label phase of the study. Patients eligible for Group 1 will be randomized to one of two treatment groups. Randomization will be stratified by disease etiology (idiopathic or diabetic), and enrollment for either of the etiologies will be capped at 60% of the total sample size. Patients eligible for Group 2 will enter the Open Label Phase of the study.
 
The study includes two phases: the screening phase and the evaluation phase. The screening phase includes a screening visit to evaluate subjects’ preliminary eligibility for the study. During the screening phase, subjects will collect diary data for at least 4 weeks. The data collected during the screening phase must be reviewed in order to determine eligibility for enrollment into the evaluation phase. Data review will be performed prior or at Visit 2. Patients who to meet all Group 1 eligibility criteria will randomized onto double blind treatment in the evaluation phase. Patients who meet Group 2 criteria or do not meet symptom criteria for randomization but still meet all other eligibility criteria, will be offered open label treatment in the open label arm of the evaluation phase. When enrollment goal is reached for

group 1, group 1 enrollment will be closed and all subsequent patients in screening will be evaluated for group 2 eligibility only.

The Evaluation Phase includes 12 weeks of double blind randomized treatment of placebo or tradipitant (85mg bid, approximately 12 hours apart) for Group 1 or open label tradipitant (85mg bid, approximately 12 hours apart) for Group 2. Daily diaries will be completed during all phases. Clinical evaluations and safety assessments will occur at Screening, Baseline, Week 2, Week 4, Week 6, Week 8, Week 10, and Week 12.

Following the End of Study Visit (Visit 8) patients can opt-in to a one-day optional pharmacokinetic (PK) study where one additional dose of tradipitant will be taken and blood will be drawn pre-dose and, 1, 2, 4, 6, 8-hour post dose to assess drug levels. This optional PK Visit can occur 1-14 days after Visit 8.

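### The adverse event tables have no rule for the optional tradipitant dose after Visit 8, so some events that follow active drug in placebo patients can be counted under placebo

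*SAP*

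**What the plan says.** The protocol synopsis, under Overall Design, offers patients an optional one-day PK study after Visit 8, "where one additional dose of tradipitant will be taken". On timing it says: "This optional PK Visit can occur 1-14 days after Visit 8". The offer is not limited by arm, and no placebo alternative is described.

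SAP 11.4.1 defines TEAEs as "those events, which are newly occurring or worsening from baseline" and sets the grouping: "Treatment-emergent adverse events will be summarized within each treatment group". The cut-off follows: "Any event starting more than 3 days after the final dose of study medication will be excluded from the above tables and only listed", with one exception, "unless the event caused discontinuation".

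Section 11.4.1 does not define treatment group. Overall Design uses the term for the randomized assignment ("Patients eligible for Group 1 will be randomized to one of two treatment groups"), and the Safety population in SAP 11.2.2 is made up of randomized, dosed subjects. I therefore take the tables to be by randomized arm, which is an inference.

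Three things are not stated: whether the PK dose is study medication for the cut-off, whether events are assigned by the treatment taken at onset, and whether events after the PK dose have a table of their own.

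**The concern.** A placebo patient who opts in takes active drug for the first time after the blinded comparison is over. The TEAE definition looks only at change from baseline, and the tables look only at the arm. Nothing in the rule separates an event that follows 12 weeks of placebo from one that follows a dose of tradipitant.

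SAP 11.4 rests the primary safety assessment largely on the frequency of TEAEs and serious adverse events (SAEs). Events after tradipitant that sit in the placebo column raise the comparator's rate. A window that depends on opting in also gives patients unequal time at risk. If the events are instead only listed, the comparison is protected, but active-drug events appear in no summary.

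**Working it through.** The plan gives no figure on this point, so there is none to reproduce. The check compares the two time windows and then sizes the effect.

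**Inputs from the documents**
- Cut-off: 3 days after the final dose (SAP 11.4.1).
- PK visit: day d = 1 to 14 after Visit 8 (synopsis, Overall Design).
- Placebo arm: 100 patients (synopsis, number of subjects).

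**Assumption on timing.** The last blinded dose falls on day L, either the day of Visit 8 (L = 0) or the day before (L = −1).

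**Reading A: the PK dose is the final dose.** The window closes at d + 3, so at the latest on day 14 + 3 = 17 after Visit 8. For patients who do not opt in it closes at L + 3, which is day 3 or day 2. Every placebo patient's event in the 3 days after the PK dose is tabulated as placebo, whichever day the visit falls on.

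**Reading B: the last Evaluation Phase dose is the final dose.** An event that starts k days after the PK dose stays in the tables if d + k − L ≤ 3.

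| Event starts | L = 0: PK days inside the window | L = −1: PK days inside the window |
|---|---|---|
| on the PK day (k = 0) | 1–3 (3 of 14) | 1–2 (2 of 14) |
| 1 day later | 1–2 (2 of 14) | 1 (1 of 14) |
| 2 days later | 1 (1 of 14) | none |
| 3 days later | none | none |

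For an event on the PK day, the remaining 14 − 3 = 11 or 14 − 2 = 12 allowed days lead to a listing only, unless the event caused discontinuation.

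**Size under Reading A.** None of these rates is in the documents. Let f be the opt-in share, r the risk of a given event after the PK dose, and b the chance that the placebo patient already had that event. With all 100 placebo patients reaching Visit 8 and independence, extra placebo patients with the event = 100 × f × r × (1 − b).

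| f | r | b = 5% | b = 10% |
|---|---|---|---|
| 10% | 5% | 0.475 | 0.45 |
| 10% | 10% | 0.95 | 0.90 |
| 25% | 5% | 1.19 | 1.125 |
| 25% | 10% | 2.375 | 2.25 |
| 50% | 5% | 2.375 | 2.25 |
| 50% | 10% | 4.75 | 4.50 |

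A true placebo rate of 5% would read between 5 + 0.475 = 5.5% and 5 + 4.75 = 9.8%.

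**Overall TEAE rate.** A subject counts once, so b is replaced by the chance p of any earlier TEAE. With p assumed at 30–60%, the range runs from 100 × 0.10 × 0.05 × 0.40 = 0.2 to 100 × 0.50 × 0.10 × 0.70 = 3.5 patients.

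**Size under Reading B.** If PK visits were spread evenly over the 14 days and events started on the PK day, the by-event range shrinks to between 0.45 × 2/14 = 0.06 and 4.75 × 3/14 = 1.0 patients.

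**Net effect between arms under Reading A.** The tradipitant arm may take the extra dose too. With the same f and r in both arms, each arm's rate x becomes x + f × r × (1 − x), so the difference is multiplied by 1 − f × r. That is a relative shrinkage of 0.10 × 0.05 = 0.5% to 0.50 × 0.10 = 5%. If only placebo patients react, because the drug is new to them, the whole increment in the table above comes off the difference.

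**The case against.** The best counter-argument is that Reading B is the more natural one. The synopsis gives treatment as lasting up to 12 weeks, calls Visit 8 the end of the study, and describes the PK day as a separate, optional study with an additional dose. On that reading, events after a PK dose on 11 or 12 of the 14 allowed days stay out of the comparative table, which is where they belong. This stands. A reader might infer that the table is wrong on either reading; the documents do not support that for the later PK days, when only a summary is missing. What survives is misattribution after an early PK visit, and a text that does not choose between the readings.

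Four other strong inferences also fail.
- That late events are lost. They are listed, and those that caused discontinuation stay in the tables. The proportions with SAEs or with events leading to discontinuation, in the last paragraph of SAP 11.4.1, are not clearly subject to the cut-off.
- That the placebo TEAE rate could rise by 10 percentage points. This needs 50% opt-in and a 20% event risk (100 × 0.50 × 0.20 = 10), with no allowance for earlier events. At p = 30–60%, once-per-subject counting cuts it to 10 × 0.70 = 7 or 10 × 0.40 = 4.
- That a bias of known size in the drug's favour is shown. The tradipitant column may also gain events, so the net effect depends on opt-in and risk in each arm.
- That laboratory, ECG and vital-sign tables are affected. The synopsis mentions only blood sampling for drug levels at the PK visit.

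Finally, SAP 11.2 calls the section general, and 11.4.1 leaves the analysis of TEAE incidence to a separate statistical analysis plan that is not available here. That plan may settle the point. But the cut-off is stated outright and is not deferred, so the separate plan would have to add a rule.

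**Conclusion.** The point holds as a gap in the rule with a probably small effect. On both readings, some events that follow tradipitant in placebo patients are tabulated under placebo: after any PK visit if the PK dose is the final dose, and after a visit on about days 1–3 (or 1–2) if it is not. Unequal windows of up to 17 against about 3 days arise only on the first reading; active-drug events without a summary arise only on the second.

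For a given event, about 0.5 to 5 extra placebo patients per 100 is a reasonable range on the first reading, with fewer for the overall TEAE rate and about 1 at most on the second. These figures rest on assumed opt-in, event and background rates, on full retention to Visit 8, and on the inference that the tables go by randomized arm.

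**What to change.** In SAP 11.4.1, or in the separate statistical analysis plan before unblinding, state that the double-blind TEAE window for Group 1 ends at the earlier of 3 days after the last double-blind dose or the time of the PK dose. Summarize events that start at or after the PK dose in a separate table, by the treatment actually received.

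This costs one sentence and one small table, and it changes nothing in trial conduct. SAP 11.2 allows method changes before database lock to be documented in the statistical analysis plan without a protocol amendment. Settling the rule before unblinding avoids choosing a column for an event once the arm is known. The downside is that a few events move out of the double-blind table, including some after early PK visits in the tradipitant arm that the current rule would count.

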11.4.2. Laboratory Data

Clinical Laboratory Data

The summary statistics of raw data (hematology and chemistry) and change from baseline values will be presented, as well as shift tables from baseline to post-baseline values using normal ranges. For urinalysis parameters, the number and percentage of subjects falling under each category of the test will be presented.

Clinical laboratory data will be summarized for each treatment group by presenting the proportions of subjects with clinically notable abnormalities ([Appendix 18](#)).

Clinically notable values will be identified according to the criteria identified in the FDA's "Supplementary Suggestions for Preparing an Integrated Summary of Safety Information in an Original NDA Submission and for Organizing Information in Periodic Safety Updates" (Revised 2-APR-87) provided by the FDA Division of Neuropharmacological Drug Products (DNDP). Differences in incidence rates between the treatment groups will be tested as described in the SAP.

11.4.3. Vital Signs and Body Measurements

Data from vital signs and body measurements will be listed, clinically notable values ([Appendix 18.2](#)) will be flagged, and any other information collected will be listed. Data will also be summarized by treatment group using mean change from baseline and proportions of subjects with values outside the normal range, and values that were clinically notable.

11.4.4. Electrocardiogram (ECG)

Results from the ECG will be listed for each subject. These data will also be summarized for each treatment group by presenting subjects with newly occurring or worsening ECG abnormalities.

11.4.5. C-SSRS

Results from the C-SSRS will be listed for each subject. These data will also be summarized by treatment group and for suicidal ideation events, suicidal behaviors and completed suicides. In particular, for each of the following suicide related events, the number and percent of subjects with the event will be enumerated by treatment group: completed suicide, nonfatal suicide attempt, interrupted attempt, aborted attempt, preparatory acts or behavior, active suicidal ideation with specific plan and intent, active suicidal ideation with some intent to act without specific plan, active suicidal ideation with any methods (no plan) without intent to act, non-specific active suicidal thoughts, and wish to be dead. Details of the analysis will be provided in the SAP.

11.5. Subgroup Analysis

The subgroup analysis (such as, gender, age, etiology, baseline illness severity etc.) for efficacy variables and safety variables may be conducted as described in the SAP.

11.6. Interim Analysis

No interim analyses are planned.

11.7. Deviations in Analysis from Statistical Plan and Other Issues

During the analysis and reporting process, any deviations from the statistical plan designed for this protocol will be described and justified in the final report.
